#### 14.4 Statistical Analysis Methods

#### 14.4.1 Overall Analytical Method

The results of this study will be analyzed and summarized using descriptive statistical methods. Measurement data will be subject to descriptive statistical analysis using mean, standard deviation, median, minimum and maximum. PK parameters will also be listed with geometric mean and coefficient of variation. Enumeration data or grade data will be expressed with frequency and frequency.

## 14.4.2 Baseline Analysis Methods

Items collected during the baseline period included:

- Subject characteristics at baseline: demographics (age, gender, ethnicity), height, weight, disease-related symptoms, ECOG score, laboratory values, gene expression or gene mutation;
- Tumor characteristics at inclusion: duration of disease, histopathological type, tumor stage, resection of primary tumor and site of tumor metastasis;
- History of prior anticancer therapy: surgery, chemotherapy, radiotherapy, or other anticancer therapy.

For continuous variables of age, height and weight, the statistics of mean, standard deviation, median, maximum and minimum of each variable are given; for categorical variables of gender and ethnicity, the frequency of each type and the corresponding percentage are given. At the same time, the medical history, other current diseases and medication were statistically described.

### 14.4.3 Analysis method of primary outcome measures

#### 14.4.3.1 Primary Outcome Measures in Part Ia

To observe the frequency of dose limiting toxicity (DLT) in subjects receiving different doses of intravenous drip of MRG003 within the first cycle. Doses at which the MTD or RP2D is inferred (see Section 6.3.4).

#### 14.4.3.2 Primary Outcome Measures in Part Ib

According to RECIST v1.1, evaluate the treatment indicators related to tumor measurement: objective response rate (ORR = 100% x (CR + PR)/total number of subjects in analysis set), and calculate the corresponding 95% CI.

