Primary study objective	
 
The primary objectives of the Phase Ia dose-escalation study are:
 
To determine the maximum tolerated dose (MTD) or recommended Phase II dose (RP2D) of MRG003
 
The primary objectives of the Phase Ib dose expansion phase of the study are:
 
To evaluate the antitumor activity of MRG003 in patients with advanced colorectal cancer, head and neck squamous cell carcinoma and nasopharyngeal carcinoma
 
		
Secondary study objectives	
 
Secondary objectives of the Phase Ia dose-escalation study:
 
To evaluate the kinetic (PK) characteristics of the drug in patients with advanced solid tumors by kinetic study;
 
To observe the safety of MRG003 in patients with advanced solid tumors;
 
To assess the immunogenicity of MRG003 in patients with advanced solid tumors;
 
To assess the antitumor activity of MRG003 in patients with advanced solid tumors.
 
Secondary objectives of the Phase Ib dose expansion phase of the study:
 
To evaluate the safety and tolerability of MRG003 in patients with advanced colorectal cancer, head and neck squamous cell carcinoma and nasopharyngeal carcinoma;
 
Evaluate the kinetic characteristics of MRG003;
 
To evaluate the immunogenicity of MRG003 in patients with advanced colorectal cancer, head and neck squamous cell carcinoma and nasopharyngeal carcinoma.
 
		
Explore trial objectives	By detecting the expression level of epidermal growth factor receptor (EGFR) in tumor pathological tissues of subjects, the correlation between EGFR and efficacy indicators will be explored.		

Number of Sites	4-8
Indications for Use	Patients with advanced solid tumors, including advanced colorectal cancer, head and neck squamous cell carcinoma and nasopharyngeal carcinoma
Subject Population	Phase Ia: approximately 26 patients with solid tumors for dose escalation to determine MTD or RP2D;  Phase Ib: 36 evaluable patients with advanced colorectal cancer, head and neck squamous cell carcinoma and nasopharyngeal carcinoma (12 patients for each group).
Overall design	First-in-human, multicenter, non-randomized, single-arm, open-label, dose escalation, dose expansion, safety, efficacy clinical trial

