# **6.5 Efficacy Assessments**

Response to tumor therapy will be assessed in this study using Response Evaluation Criteria in Solid Tumors RECIST v1.1, see Appendix II.

The primary outcome measure of Ib trial is objective response rate (ORR), the proportion of subjects with confirmed overall CR and confirmed overall PR in all subjects who have received the study drug.

Progression-free survival (PFS) for this study is defined as the time from the start of treatment with MRG003 until objective tumor progression or death from any cause. Duration of response (DOR) is defined as the time from the first documented response until disease progression or death among subjects with a confirmed objective response (CR or PR), with tumor evaluation according to RECIST v1.1 criteria. Overall survival (OS) is defined as the time from the start of treatment with MRG003 to death due to any cause.

For patients without disease progression after the last dosing cycle, tumor response should be assessed every 6 weeks and followed up for survival until disease progression or other anti-tumor treatment. Survival follow-up could be performed every 12 weeks after confirmation of disease progression or receipt of additional antineoplastic therapy. The follow-up period starts from the end of treatment cycle until death or study termination. During follow-up, survival status and subsequent tumor treatment need to be examined and recorded. Subsequent tumor treatment does not need to be recorded in electronic case report form (eCRF).

Tumor evaluation will be performed according to RECIST v1.1, and the results of imaging assessment methods should be recorded in the electronic case report form. During trial treatment, radiographic assessments may be performed  $\pm$  7 days from the scheduled date and the methodology should be consistent between baseline and subsequent follow-up. Whenever clinically permissible, the same oral or intravenous contrast agent was used for each scan, and, whenever possible, the same investigator/radiologist evaluated all patient scans during the study.

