# 7 TRIAL, WITHDRAWAL, DISCONTINUATION

# 7.1 Number of subjects

Part Ia: Approximately 26 patients with solid tumors will participate in the dose escalation study to determine MTD/RP2D;

Part Ib: 36 evaluable patients with advanced colorectal cancer, 12 patients with head and neck squamous cell carcinoma and 12 patients with nasopharyngeal carcinoma.

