## 14 STATISTICAL ANALYSIS

#### 14.1 Sample Size

The number of patients with advanced solid tumors in Phase Ia needs to be determined based on the results of patient safety evaluation in the actual dose escalation trial. The expected number of patients is approximately 26.

A total of 36 patients (12 in each category) with advanced colorectal cancer, head and neck squamous cell carcinoma, and nasopharyngeal carcinoma were evaluable for the phase Ib trial. Since this study is an exploratory Phase I clinical trial, the number of patients participating (i.e., sample size) is not based on formal statistical calculations.

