#### 14.3 Data Analysis Set

Safety Set (SS): includes all subjects who received at least one treatment. Safety analysis set is used for safety analysis and primary analysis of efficacy indicators.

Evaluable Analysis Set: Phase Ia includes subjects who have at least one post-treatment tumor assessment; Phase Ib includes subjects who have not achieved CR and PR response and have at least one evaluable baseline post-treatment tumor assessment, and subjects who have achieved CR and PR response include at least two post-treatment tumor assessments (and are at least 4 weeks apart). The evaluable analysis set was used for secondary analyses of efficacy measures.

PK Analysis Set (PKS): includes subjects who received at least one treatment and had at least one valid post-treatment PK concentration measurement. The PK analysis set was used for the analysis of PK parameters.

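### Section 7.1 gives the Phase Ib cohorts as 36 + 12 + 12 against 12 + 12 + 12 elsewhere, and the primary ORR is not stated by tumour type

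*Protocol*

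**What the plan says.** **Cohort sizes.** The Subject Population entry of the synopsis plans "36 evaluable patients with advanced colorectal cancer, head and neck squamous cell carcinoma and nasopharyngeal carcinoma (12 patients for each group". Section 14.1 agrees: "A total of 36 patients (12 in each category) with advanced colorectal cancer, head and neck squamous cell carcinoma, and nasopharyngeal carcinoma were evaluable". Section 6.1 gives 36 for the three cancers together, without a split. Section 7.1, the section on the number of subjects, reads instead "36 evaluable patients with advanced colorectal cancer, 12 patients with head and neck squamous cell carcinoma and 12 patients with nasopharyngeal carcinoma".

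**Primary ORR.** Section 5.1 gives the Phase Ib primary objective as antitumour activity in patients with colorectal cancer, head and neck squamous cell carcinoma and nasopharyngeal carcinoma. Section 6.5 defines ORR as "the proportion of subjects with confirmed overall CR and confirmed overall PR in all subjects who have received the study drug". Section 14.3 names the set: "Safety analysis set is used for safety analysis and primary analysis of efficacy indicators". Section 14.4.3.2 gives the calculation: "objective response rate (ORR = 100% x (CR + PR)/total number of subjects in analysis set), and calculate the corresponding 95% CI". None of these places says whether the rate is computed within each tumour type or across all three.

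**Inference.** The synopsis describes the analysis as descriptive, without statistical tests. Section 14.1 says the sample size rests on no formal calculation.

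**The concern.** Section 7.1 is operative text. A site or ethics committee that reads it alone would take the colorectal cohort to be three times its size in Section 14.1. A statistical analysis plan cannot repair a wrong enrolment number in the protocol.

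The second issue is the match between the primary measure and the objective. The trial fills three cohorts of fixed, equal size in three named cancers, so the natural estimate is a response rate in each. The sections that define the primary measure name only an overall denominator and one interval. If they are followed literally, the primary result is an average over three diseases weighted by cohort size. Such an average can sit well away from the rate in any of them, and Section 6.1 expects Phase I to supply preliminary efficacy results for Phase II.

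**Working it through.** **1. Cohort sizes.** Inputs are the counts in the synopsis and Sections 6.1, 7.1 and 14.1.

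- Synopsis and Section 14.1: 3 × 12 = 36. This reproduces the stated total and agrees with Section 6.1.
- Section 7.1, read literally: 36 + 12 + 12 = 60.
- Difference: 60 − 36 = 24, all in the colorectal cohort (36 against 12, a factor of 3).

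The likely cause is a lost phrase giving the colorectal number. With 36 as the total and 12 for each cancer, Section 7.1 would match the other places.

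**2. What one ORR can show.** The protocol has no target response rate, power or alpha to reproduce. The response counts below are illustrative and are not protocol figures. Two further assumptions are that exactly 12 subjects per tumour type are treated, and that the interval is Clopper-Pearson, since Section 14.4.3.2 names no method.

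For x responders of n, the lower limit is the 2.5% quantile of Beta(x, n − x + 1) and the upper limit is the 97.5% quantile of Beta(x + 1, n − x). The lower limit is 0 when x = 0.

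Three splits of nine responders over cohorts of 12:

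| Responders per 12 | Overall | ORR by tumour type (exact 95% CI) |
|---|---|---|
| 3 / 3 / 3 | 9/36 = 25% (12.1 to 42.2%) | 25% (5.5 to 57.2%) in each |
| 0 / 3 / 6 | 9/36 = 25% (12.1 to 42.2%) | 0% (0 to 26.5%); 25% (5.5 to 57.2%); 50% (21.1 to 78.9%) |
| 0 / 0 / 9 | 9/36 = 25% (12.1 to 42.2%) | 0% (0 to 26.5%) twice; 75% (42.8 to 94.5%) |

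The overall column is identical in all three rows, while the rate in a single cohort runs from 0% to 75%. In the last row the overall interval ends at 42.2%, just below the 42.8% at which the active cohort's interval begins.

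**3. The price of splitting.** At 25%, the interval is 42.2 − 12.1 = 30.1 percentage points wide on 36 subjects and 57.2 − 5.5 = 51.7 points wide on 12. For 6/12 it is 78.9 − 21.1 = 57.8 points.

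**The case against.** The strongest reply is that the protocol never says the cancers are pooled. The expression in Section 14.4.3.2 is a generic definition of a rate. Section 14.4.4.1 uses the same one for Phase Ia, which spans eight planned dose levels. It can be applied within each cohort without changing a word, and Section 14.1 plainly recognises the cohorts. Section 14.2 leaves detailed steps to a separate analysis plan that is not shown here, and tabulation by cohort is often placed there. This stands to the extent that the text is unspecific; it does not commit the trial to a pooled analysis. It does not remove the point, because the protocol states a denominator, and that denominator, taken literally, covers all treated subjects.

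A reader might infer three stronger things that the documents do not support:

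- *That pooling is the declared primary analysis.* No section says so.
- *That Phase Ia subjects enter the denominator, because the Safety Set is not defined by phase.* The heading of Section 14.4.3.2 confines it to Part Ib, and Section 6.5 ties ORR to the Ib trial.
- *That the Ib response rate is the rule for choosing Phase II indications.* Section 6.1 speaks only of preliminary results for Phase II.

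It is also tempting to carry the 36/12/12 mix into an overall ORR and report how far it moves. That mix contradicts every other statement of the design, and the direction of the shift depends on which cancer is assumed to respond least, so the exercise shows nothing useful.

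On Section 7.1, the reply is that the slip is obvious and the other sections settle the intended number. That is fair as to intent, but the section is still wrong as written.

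**Conclusion.** The cohort-size contradiction is certain and rests on no assumption: Section 7.1 reads as 60 patients where the synopsis and Sections 6.1 and 14.1 say 36.

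The ORR part holds as a failure to specify. Sections 6.5 and 14.4.3.2, read literally, yield one Phase Ib rate and interval and do not state the rate by tumour type, while the objective and the 12-per-group design point to a rate in each. The size of what could be hidden depends on the responses. In the illustration, an overall 25% is compatible with cohort rates anywhere from 0% to 75%. That rests on assumed counts, 12 treated subjects per type and exact intervals. No power, alpha or test is affected, because the trial is descriptive; what is affected is the meaning of the primary result. The change should be made, but nothing here calls the design itself into question.

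**What to change.** - **Section 7.1:** state 36 evaluable patients in Phase Ib, 12 with colorectal cancer, 12 with head and neck squamous cell carcinoma and 12 with nasopharyngeal carcinoma, matching the synopsis and Section 14.1.
- **Section 14.4.3.2:** state that confirmed ORR is reported for each tumour type, with all treated Phase Ib subjects of that type as denominator and an exact (Clopper-Pearson) 95% CI, and that any overall Phase Ib ORR is supportive. Section 6.5 needs a matching phrase.

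The cost is a few lines of text and one results column per tumour type. No patients, visits or tests are added. The downside is the wider interval at n = 12 shown above, which reflects how much 12 patients can say about one cancer.

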## 14.4.4 Analysis method of secondary outcome measures

#### 14.4.4.1 Secondary Outcome Measures in Phase Ia

- PK parameters of all subjects in the three components of MRG003 were analyzed by non-compartmental method during the dosing period, but not limited to Cmax, Tmax, t1/2, MRT, Vd, CL, AUC0-t and AUC0-inf.
  - Drug safety and tolerability were evaluated. Descriptive statistical methods were used to analyze and summarize the type, severity, occurrence time, frequency and correlation of adverse events with the study drug.
    - Anti-therapeutic drug antibody (ADA) analysis: Descriptive statistical analysis was performed using the percentage of ADA positive, and the range of each ADA positive subject was listed.
    - After intravenous drip of MRG003 at different doses every two treatment cycles, the best efficacy response, complete response (CR), partial response (PR), stable disease (SD), progressive disease (PD) and non-evaluable (NE), was assessed in subjects throughout the trial. The number and proportion of subjects with each response will be summarized and described. Confirmation of two response evaluations is not required for best response in Phase Ia. If a subject has stable disease (SD) as their best response, SD must be evaluated at least 5 weeks after the first dose. The objective response rate (ORR = 100% x (CR + PR)/total number of subjects in the analysis set) and its corresponding 95% CI will be calculated.

#### 14.4.4.2 Secondary Outcome Measures in Phase Ib

- Drug safety and tolerability will be assessed. Descriptive statistical methods will be used to analyze and summarize the types and severity of adverse events and their correlation with the study drug.
- At MTD/RP2D, within the treatment cycle of intravenous drip of MRG003, determine the concentrations of the three drug components in all subjects, and calculate the drug PK values, not limited to Cmax, Tmax, t1/2, MRT, Vd, CL, AUC0-t and AUC0-inf; perform kinetic analysis according to non-compartment model; evaluate the concentration and pharmacokinetic parameter pharmacokinetic analysis software.
  - Anti-therapeutic drug antibody (ADA) analysis: Descriptive statistical analysis was performed using the percentage of ADA positive, and the range of each ADA positive subject was listed.
- To assess the best response of subjects throughout the trial according to RECIST v1.1 criteria: complete response (CR), partial response (PR), stable disease (SD), progressive disease (PD) and non-evaluable (NE). The number and proportion of subjects in each efficacy endpoint will be summarized and described. The best response in Phase Ib requires confirmation by two assessments.

• To assess tumor efficacy measures in relation to time: progression-free survival (PFS), overall survival (OS), and duration of response (DOR). The product limit method was used to calculate the estimated survival time and 95% confidence interval, and the survival time and its confidence interval in the first and third quartiles (Q1, Q3). Survival curves were plotted with the Kaplan-Meier method.

#### **14.4.5 Safety Analysis Methods**

For safety analysis, descriptive statistics will be used to summarize incidence of adverse events (AEs) and calculate normal/abnormal changes of laboratory test results before and after treatment. The listing of various AEs and the listing of clinically significant abnormalities in laboratory parameters after treatment will be detailed.

Safety indicators will include adverse events, vital signs (blood pressure, pulse and body temperature) and laboratory data. Safety analysis will be based on Safety Analysis Set (SS).

The analysis of adverse events in the safety analysis only analyzed treatment-emergent adverse events (TEAEs). For adverse events (TEAEs) during the treatment period, all AEs occurred within 21 days after the last dose, and adverse events and serious adverse events were collected. Adverse events will be summarized, and the number and percentage of patients with adverse events and the number of events will be calculated, classified by MedDRA preferred term, and severity will be determined based on CTCAE v.4.03 grading. The list of adverse events will be listed according to the occurrence time of adverse events of subjects, the treatment period where they are located, and the CTCAE grade of adverse events.

Hematological toxicity was assessed with laboratory parameters. Neutropenia, thrombocytopenia, and anemia were graded by CTCAE and calculated according to the National Cancer Institute (NCI) Common Terminology Criteria. Qualitative and quantitative results of hematological toxicity will also be summarized.

The blood biochemical indicators of the subjects were assessed according to the blood biochemical reference values of the study hospital. Blood biochemical indicators were analyzed and summarized according to CTCAE grade.

#### 15 QUALITY ASSESSMENT AND MANAGEMENT

The principal investigator and the clinical study institution allow the CRO, sponsor, ethics committee/clinical institution review committee and authorized representatives of government regulatory authorities to monitor, audit and inspect the clinical trial. These authorized representatives may also review the original clinical study documents and data directly.

## **15.1 Trial Monitoring**

The monitor should contact and visit the investigator regularly to evaluate the progress of the trial and the compliance with GCP, regulations and trial protocol, and collect and confirm the authenticity, accuracy and comprehensiveness of the data recorded in the eCRF. The investigator and the personnel involved in the trial should cooperate with the monitor to ensure that the problems that may be found are resolved.

#### 15.2 Trial Audits

The main purpose of the audit is to confirm that the rights and safety of patients are protected, and that all data related to the evaluation of investigational drugs are operated and reported in accordance with GCP and relevant administrative regulations. Covance Pharmaceutical R & D (Beijing) Co., Ltd. is responsible for auditing the implementation of clinical trials to assess compliance with the Good Clinical Practice (GCP).

#### 15.3 Study inspection

Government regulatory authorities may also initiate an inspection of a clinical trial during or after the trial is completed, and if the investigator receives such notice, he/she should immediately notify Shanghai Miracogen Inc. to cooperate with the relevant work.

This clinical trial will be conducted in accordance with the Declaration of Helsinki (2000 Edition) and the relevant Good Clinical Practice and regulations in China. The study protocol can be implemented only after approved by the Ethics Committee of Sun Yat-sen University Cancer Center before the study is initiated. If this trial involves multiple clinical study sites, the Ethics Committee of each clinical study site shall approve the clinical trial protocol to be implemented in that site. The investigator and sponsor were not able to dispense study drug and the investigator was not able to initiate the study until written and dated approval/consent was obtained. During the clinical trial, any amendment to the trial protocol should be approved or filed by the Ethics Committee before implementation. Any event that is likely to affect the safety of patients or the continuation of the clinical trial, especially any change in safety, should also be reported to the Ethics Committee. Any update to the Investigator's Brochure should be submitted to the Ethics Committee. The clinical investigator must inform the subject that participation in the clinical trial is voluntary, that the subject has the right to withdraw from the trial at any stage of the trial without discrimination or retaliation, that his/her medical treatment and rights and interests are not affected, and that he/she can continue to receive other treatment or treatment. The subjects must be informed that the personal data of participating in the trial and during the trial are confidential. The subject should be informed of the nature of the clinical trial, the purpose of the trial, the expected possible benefits and possible risks and inconveniences, and of other treatment options available to the subject and the rights and obligations of the subject in accordance with the Declaration of Helsinki, so that the subject can have sufficient time to consider whether he/she is willing to participate in the trial,

